5.1.2 Ceftobiprole dosing (Day 1)

The ceftobiprole dose should be scheduled so that the infusion and subsequent assessments (see [Table 3](#)) do not conflict with the ongoing therapy with systemic antibiotics, or routine care.

Ceftobiprole medocartil must be reconstituted and diluted for intravenous (i.v.) administration as described in Section 6.2. Briefly, a single infusion of ceftobiprole medocartil will be given at 7.5 mg/kg (calculated as ceftobiprole mg equivalents; see Section 6.1), in a weight-adjusted volume of infusion solution given as a constant rate over 4 hours. The date and exact start and stop times of the infusion will be entered into the eCRF.

Ceftobiprole must be administered via a separate infusion line. No other intravenous infusion may be given through the same line during the 4-hour ceftobiprole infusion, and – if feasible – attempts should be made to not simultaneously administer any other antibiotic treatment (i.e., through any infusion line) during the ceftobiprole infusion. If feasible, attempts should be made to allow for a minimum period of 30 minutes between the end of administration of any other antibiotic treatment and the start of ceftobiprole medocartil infusion. Body weight measured on Day 1 will be used for dose calculation and should be obtained within 6 hours prior to dosing.

Blood samples (200–300 µL) and urine (if possible) for PK analysis will be collected and prepared (see Sections 5.2.2.1 and 5.2.2.2, respectively), at times described in Table 3.

A physical examination will be performed on Day 1 and body weight will be obtained, unless physical examination and body weight were obtained during the screening evaluation within 6 hours prior doing on Day 1.

Vital signs will be recorded at times described in Table 3.

After completion of the ceftobiprole infusion, an aliquot of approximately 3 mL of infusion solution will be collected and sent for analysis as described in Appendix 2.

Changes in medication will be recorded. Adverse events will be monitored and recorded continuously throughout the study (see Table 2 and Section 5.2.3.1).

5.1.3 Follow-up assessment (Day 7±3)

Each subject will be evaluated for safety on Day 7 ± 3 after ceftobiprole dosing. Safety assessments will comprise physical examination, vital signs, safety laboratory tests (haematology, clinical chemistry, and urinalysis; see Section 5.2.3.2), and AEs.

5.2 Study procedures

5.2.1 Efficacy

The efficacy of ceftobiprole will not be assessed in this study.

5.2.2 Pharmacology

5.2.2.1 Collection and preparation of blood samples

Blood samples of 200–300 µL will be obtained for PK analysis at the times described in Table 3.

The date and exact times of blood sampling will be entered into the eCRF.

Blood for PK analysis should preferably be collected from a vein in the contralateral arm to that used for the i.v. administration of ceftobiprole; however collection may be at any site other than the infusion site, including heel prick sampling or collection through a central line, if available.

Blood samples will be immediately transferred into pre-chilled tubes containing citric acid and EDTA as a coagulant. Samples will be centrifuged, and the supernatant will be frozen and kept at below –65 °C until shipment. Frozen samples will be shipped to the sponsor as described in Appendix 2.

Details on handling of PK samples are provided in the Pharmacokinetics Manual for this study (provided separately).

5.2.2.2 Collection and preparation of urine samples

Attempts should be made to obtain urine at the times described in Table 3.

Full portions of urine will be collected in subjects in whom a urinary catheter has been placed for their standard clinical care. For more details see the Pharmacokinetics Manual

for this study (provided separately). Urinary catheters will not be placed for the purpose of the study.

In subjects without a urinary catheter one or more portions of urine may be obtained at any time during the periods indicated in Table 3, and the date and exact time of sample collection will be entered into the eCRF. The total amount of collected urine should be stabilized with citric acid, frozen and kept at below $-65\text{ }^{\circ}\text{C}$ until shipment. Frozen urine should be shipped to the sponsor as described in Appendix 2. For details see the Pharmacokinetics Manual for this study (provided separately).

5.2.2.3 Analysis of ceftobiprole concentrations

Plasma and urine concentrations of ceftobiprole medocartil, ceftobiprole, and of the open-ring metabolite (BAL1029), will be quantified by means of a validated liquid-chromatography/ tandem mass spectrometry (LC-MS/MS) method.

5.2.2.4 Pharmacokinetic parameters

Plasma and urine samples will be analysed for concentrations of ceftobiprole, and if applicable for concentrations of ceftobiprole medocartil and the open-ring metabolite (BAL1029). The analysis will be performed using validated gradient reversed-phase liquid chromatography coupled with a tandem mass spectrometer (LC/LC-MS/MS); analysis will be carried out under the supervision of the sponsor.

Calibration and quality control (QC) samples will be prepared in blank and pre-tested human plasma or urine, and will be subject to the same assay procedure as experimental samples. The limit of quantification (LOQ) will be defined as the lowest concentration of analyte in a human plasma or urine sample, which can be quantitatively determined with inter-assay precision and accuracy of $100 \pm 20\%$. Lower concentrations will be denoted as 'BLQ' (below limit of quantitation). Assay performance will be controlled by the analysis of QC samples. When calculating mean drug levels for a subject cohort, if $< 50\%$ of samples are BLQ, drug levels in these samples will be set to zero. If $\geq 50\%$ of samples are BLQ, no mean value will be calculated.

Time-concentration profiles of ceftobiprole in plasma will be analysed by use of non-compartmental models. Actual sampling times will be used in all calculations. The following PK parameters will be determined for each individual, cohort, and by post-natal age:

C_{\max}	The observed maximum plasma concentration.
$t_{1/2}$	The apparent terminal elimination half-life, calculated by $t_{1/2} = \ln 2/\beta$, where β is the elimination rate constant, estimated by linear least squares regression of the plasma concentration versus time data in the terminal elimination phase.
AUC_{0-t}	The area under the plasma concentration-time curve from time zero to the last sampling time with a concentration above the LOQ. AUC_{0-t} will be calculated according to the linear trapezoidal rule.
$AUC_{0-\infty}$	The area under the plasma concentration-time curve from time zero to infinity, estimated from $AUC_{0-t} + C_t/\beta$, where t is the last sampling time with a concentration above the LOQ.
CL_S	The total systemic clearance, estimated by $CL_S = \text{dose}/AUC_{0-\infty}$.
V_{SS}	The apparent volume of distribution at steady state, estimated by $V_{SS} = (\text{dose} \times AUMC/AUC^2) - (\text{dose} \times T/2AUC)$, where AUMC is the area under the first moment curve and T is the infusion

	time.
T > MIC	The length of time plasma concentrations of ceftobiprole exceed the MIC (4 µg/mL).

Concentrations of ceftobiprole, ceftobiprole medocaryl, and open-ring metabolite (BAL1029) in urine will be determined; these results will be analysed by use of descriptive statistics. If a sufficient number of samples are available, parameters of urinary excretion may be determined.

The relationship between exposure (C_{max} and AUC), derived PK parameters (CL_S , V_{SS} , $t_{1/2}$) gestational age, post-natal age, body weight, body mass-index, body surface area, and calculated creatinine clearance will also be assessed.

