8 STATISTICAL CONSIDERATIONS

8.1 Primary and secondary study variables

The primary study variables are PK parameters C_{\max} , $AUC_{0-\infty}$ and $T > MIC$ (presuming an MIC of 4 $\mu\text{g/mL}$).

Secondary variables comprise other PK parameters (see Section 5.2.2.4), and safety variables as described in Section 5.2.3.

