The modeling strategy was to optimize the dosing regimen (dose, dosing interval and infusion duration) for paediatric subjects > 3 months to < 2 years in order to maximize $fT > MIC = 4$ µg/mL and maintain exposure in the range well tolerated by adults, and below the exposure at the NOAEL in the juvenile rat study [9] for the corresponding age groups. Several variables were explored: incremental higher doses (up to 25 mg/kg), infusion times (2 or 4 hours), dosing regimen (q6h or q8h), and combinations of these variables. Total and unbound parameters were generated using a free fraction of 0.84 as reported in adults. The optimized dosing regimen for the age group of ≥ 3 month to < 2 years was 20 mg/kg as a 4-h infusion q8h from an exposure/PD and safety point of view as summarized in Table 7. Exposure in this age group at the recommended dose of 20 mg 4-h infusion q8h is 2 to 3-fold lower than the exposure obtained at the NOAEL in the juvenile toxicity study for Day 1 post-partum pups.

Table 7 Predicted exposure to ceftobiprole in the age group ≥ 3 months to < 2 years

Number of subjects (N=16)	
Ceftobiprole dose of 20 mg/kg 4-h infusion q8h	
$fT > MIC = 4 \mu\text{g/mL}$ below 50% of dosing interval	0
Above highest adult C_{max}	0
Above highest adult AUC	1
Above exposure (C_{max} and AUC) at NOAEL	0

A PK model developed for neonates and infants was based on the fact that ceftobiprole is eliminated by the kidneys, and approximately 90% of the dose is recovered unchanged in urine, distribution is restricted to the extracellular compartment, and the systemic clearance of ceftobiprole correlated (coefficient of correlation of 0.9858) with the creatinine clearance in a dedicated clinical pharmacology study in renally impaired subjects. The model provided estimates for exposure and urinary concentration presented in [Table 8](#).

Table 8 Estimated normal and worst-case exposure and urinary concentrations following a single dose of 7.5 mg/kg ceftobiprole in neonates and infants up to a postnatal age of 3 months.

PNA	Dose (mg)	Normal condition			Worst-case			Dose (mg/h)	Urine output (mL/h)	Urine conc. (mg/mL)
		S_{cr} (mg/dL)	$T_{1/2}$ (h)	AUC ($\mu\text{g}\cdot\text{h}/\text{mL}$)	S_{cr} (mg/dL)	$T_{1/2}$ (h)	AUC ($\mu\text{g}\cdot\text{h}/\text{mL}$)			
8 d	25.7	0.38	2.3	63.2	1.10	10	189.3	6.4	7	0.94
15 d	27.4	0.35	2.2	60.5	1.10	11	189.8	6.9	7	0.94
1 mo	30.5	0.28	1.9	50.5	0.88	9	157.1	7.6	8	0.94
2 mo	37.7	0.25	1.9	51.6	0.88	10	182.5	9.4	10	0.94

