- Laboratory normal ranges (enzymatic method):

	Creatinine (mg/dL)	
UZ Leuven	0.31 – 0.88 (< 1 month)	0.16 – 0.39 (1–12 months)
AZ Sint-Jan	0.24 – 0.85 (< 2 month)	0.17 – 0.42 (2–12 months)

Abitbol¹² reported creatinine levels of 0.68 ± 0.14 mg/dL during postnatal day 3–7 in 60 preterm infants (34±3 weeks). The same report presented a graph of eGFRs calculated with the modified Schwartz formula, in which the values of all age groups were greater than 20 mL/min/ 1.73 m². Of note, the creatinine-based equation underestimated the GFR compared to the CysC-based equations, especially in pre-term neonates.

- In the meropenem PK study published by Van den Anker¹³, a creatinine level of greater than 140 µmol/L (= 1.58 mg/dL) led to the exclusion of the subject from the study.
- Two graphs presented at an EMA Workshop on regulatory and scientific issues related to the investigation of medicinal products intended for neonate use¹⁴ indicated that creatinine levels in neonates of more than 1000 g body weight, or a GA of more than 27 weeks, fell from a maximum of about 110 µmol/L on day 1 to about 50 µmol/L within 3 to 4 weeks.

Conclusion

Serum creatinine levels are generally used to monitor renal function.¹⁰ GFR is indirectly proportional to creatinine, i.e. a GFR of 2/3 of normal corresponds to a 1.5-fold higher than normal creatinine level. Since PMA is the best parameter of kidney maturation, the following creatinine thresholds (determined with the enzymatic method) may be used to support the evaluation of exclusion criterion 5:

PMA (weeks)	Creatinine (mg/dL)	Rationale
28–34 completed	1.32	150% of the upper limit of the laboratory normal ranges
35–42 completed	1.1	Arithmetic mean of 1.32 and 0.88
> 42	0.88	Upper limit of the laboratory normal ranges of the lower age groups and slightly more than 150% of 0.5 mg/dL, the stable creatinine level during the first 2 years of life

¹² Abitbol CL et al (2014) Neonatal kidney size and function in preterm Infants: What is a true estimate of glomerular filtration rate? J Pediatr 164:1026-31).

¹³ Van den Anker JN, et al (2009) Meropenem pharmacokinetics in the newborn. AAC 53(9):3871

¹⁴ Van den Anker (2006) Workshop on Regulatory and Scientific Issues related to the Investigation of Medicinal Products intended for Neonatal Use

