2.3.1.1 Cohorts

The study population was initially planned to comprise of 3 cohorts, with 15 subjects in each cohort, based on gestational age (28 to 32 weeks [Cohort 3]; 33 to 36 weeks [Cohort 2]; ≥ 37 weeks [Cohort 1]).

Due to the very low rate of patient recruitment, only cohort 1 was successfully completed. There is no cohort 2 and cohort 3 population at the end of the study.

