5 STATISTICAL PLAN AND METHODS

The statistical analysis will be performed using the software package SAS version 9.3 or higher (SAS Institute Inc., Cary, NC 27513, USA). Validation will be done by double programming.

All individual data as well as results of statistical analyses will be presented in individual patient data listings and statistical summary tables.

In general, continuous variables will be summarized using the following standard descriptive summary statistics: mean, standard deviation, median, minimum, maximum and number of observations. Categorical data will be described using frequency and percentage. Shift tables will be provided, where appropriate. One additional decimal point for mean, median, Q1, Q3 and two additional decimal points for SD will be used.

PK parameters will be presented by individual listings and descriptive summary statistics including arithmetic and geometric means, arithmetic and geometric coefficients of variation, standard deviation, minimum, median, and maximum.

Percentages will be rounded to one decimal place or more if most results are close to 0 or 100. Unscheduled assessments will only be listed and will not be included in the tables, unless otherwise specified. Any changes in the planned statistical methods will be documented in the clinical study report.

To assess the relationship between pairs of continuous variables (including PK parameters), the Pearson product moment correlation will be computed. This will however, only be applied when each variable has at least 5 non-missing observations. This correlation computation will apply to C_{max} , AUC, CL_s , V_{ss} , $t_{1/2}$, gestational and post-natal age, weight, BMI, BSA, and calculated creatinine clearance.

The following international dictionaries will be used for medical coding:

- Medical History events: MedDRA (version 20.1)
- Medications: WHO Drug Dictionary Enhanced (March 2018 B2 version)
- Adverse events: MedDRA (version 20.1)

Data from all participating study centers will be combined for analysis.

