5.4.1.1 Pharmacokinetic analysis

Plasma concentrations at each time point of measurement will be evaluated by descriptive statistics, including arithmetic mean, standard deviation (SD), minimum, maximum, and median. Actual sampling times will be used to calculate PK parameters. If $\leq 50\%$ of the values at a given time point are BLQ, these values will be set to zero for mean value calculation. If more than 50% of the values at a given time point are BLQ, no mean value will be calculated. Mean plasma concentration profiles of cohort 1 will be generated according to these criteria.

For PK evaluation, BLQ-values at infusion start will be set to zero, BLQ-values at the end of the sampling period will be disregarded for PK assessment. Single BLQ values during blood sampling will be taken as 'missing values', if the following sample(s) show a concentration above the BLQ value.

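### The terminal slope is defined by regressing concentration, not log concentration, on time, so half-life and AUC to infinity are dimensionally invalid as written

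*Protocol*

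**What the plan says.** Protocol 5.2.2.4 sets t1/2 = ln2/β, calls β the elimination rate constant, and says it is "estimated by linear least squares regression of the plasma concentration versus time data in the terminal elimination phase". The AUC0-∞ entry ("The area under the plasma concentration-time curve from time zero to infinity") is AUC0-t + Ct/β, and CLs is dose/AUC0-∞. Vss uses AUC and AUMC.

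Protocol 8.1 gives the status of these quantities: "The primary study variables are PK parameters" Cmax, AUC0-∞ and T>MIC at 4 µg/mL. The other PK parameters are secondary.

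The SAP does not define β. Section 2.2.3 lists parameter names. Section 5.4.1.1 says "Actual sampling times will be used to calculate PK parameters" and gives rules for values below the limit of quantitation. Section 5 plans Pearson correlations ("This correlation computation will apply to" Cmax, AUC, CLs, Vss, t1/2, the two ages, body-size measures and calculated creatinine clearance). Section 2.3.1.1 reports that "only cohort 1 was successfully completed", so the analysis concerns infants of gestational age 37 weeks or more. The separate Pharmacokinetics Manual is cited for sample handling, not for parameter estimation.

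**The concern.** During first-order elimination ln(concentration) falls linearly with time, and minus that slope is the rate constant, in 1/h. Raw concentration does not fall linearly, and its slope is not a rate constant. Protocol 5.2.2.4 is the only definition of β in the text supplied, and it names the raw regression. A programmer therefore has to infer the log scale against the wording.

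If the rule were programmed as written:

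- half-life would change with the concentration unit and could be wrong in either direction;
- AUC0-∞ would be too low, and CLs too high, in infants who clear the drug slowly;
- the planned correlations of t1/2 and CLs with creatinine clearance and age would be distorted.

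Cmax, AUC0-t and T>MIC within the 12 h of sampling do not use β.

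**Working it through.** **Dimensions.** The slope of C (µg/mL) on t (h) is in µg/mL/h. Then ln2/β is in h/(µg/mL), not h. Ct/β is in h and cannot be added to AUC0-t in µg·h/mL. Multiplying all concentrations by 1000 (µg/mL to ng/mL) divides the literal half-life by 1000. With ln C on t, β is in 1/h and all three formulas are consistent.

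**Illustration: inputs.** The protocol reports no half-life or AUC obtained by this rule, so there is no figure to reproduce. I used:

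- dose, half-life and AUC from each row of Table 8 in Protocol Appendix 1 ("Estimated normal and worst-case exposure and urinary concentrations"): normal rows t1/2 1.6–2.3 h and AUC 42.8–63.2 µg·h/mL, worst-case rows t1/2 9–11 h and AUC 157.1–189.8 µg·h/mL;
- the protocol's 4 h infusion, samples at 0, 2, 4, 6, 8 and 12 h, and linear trapezoids;
- an assumed noise-free one-compartment profile.

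The protocol does not say which points form the terminal phase, so I ran both 4–12 h and 6–12 h.

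**Formulas.** CL = dose/AUC; k = ln2/t1/2; V = CL/k. During the infusion C(t) = (dose/4)/CL × (1 − e^(−kt)); after it C(t) = C(4) × e^(−k(t−4)).

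**Worked row: 8 days, worst case (dose 25.7 mg, AUC 189.3, t1/2 10 h), 6–12 h window.** CL = 25.7/189.3 = 0.136 L/h. C at 6, 8 and 12 h is 9.98, 8.68 and 6.58 µg/mL. AUC0-12 = 94.3.

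- Literal β = 0.560. The half-life is 0.693/0.560 = 1.24. AUC0-∞ = 94.3 + 6.58/0.560 = 106.1, which is 44% below 189.3. CLs = 25.7/106.1 = 0.242 L/h, 78% too high.
- Log-scale β = 0.0693. The half-life is 10.0 h. AUC0-∞ = 94.3 + 6.58/0.0693 = 189.3.

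**Table 8 rows and variants, µg/mL, range over both windows.**

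| Profile | True t1/2 (h) | Literal t1/2 | AUC0-∞ error | CLs error |
|---|---|---|---|---|
| Normal rows | 1.6–2.3 | 0.58–1.29 | −3.0% to +0.8% | −0.8% to +3.1% |
| Worst-case rows | 9–11 | 1.1–1.4 | −40% to −47% | +66% to +88% |
| Worst-case AUC, V held at the row's normal value | 5.9–6.9 | 0.63–0.73 | −27% to −33% | +38% to +50% |

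The third line is there because the worst-case rows of Table 8 imply a larger V than the normal rows (for example 1.96 against 1.35 L at 8 days).

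**Milder slowing.** With the 8-day normal V, true half-lives of 3, 4 and 5 h give AUC0-∞ about −7%, −15% and −22%, and CLs about +8%, +17% and +28%.

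**Does the literal half-life track elimination?** With the 8-day normal V and the 4–12 h window, true half-lives of 2.3, 3, 4, 5 and 6.9 h give 0.58, 0.55, 0.55, 0.58 and 0.65. It hardly moves. The error can also go the other way: a true 1.6 h with an assumed AUC of 30 µg·h/mL (3-month dose, 6–12 h window) gives 1.85.

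**Unit.** The 8-day normal profile gives 0.58 in µg/mL and 0.0006 in ng/mL (4–12 h). In ng/mL, Ct/β almost vanishes and AUC0-∞ collapses to AUC0-12: the error is −0.4% to −4.3% in the normal rows and −46% to −53% in the worst-case rows.

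**With the log slope.** Half-life is exact in every row, and AUC0-∞ is within about 1%. What remains is trapezoid error.

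**Could slow eliminators be in Cohort 1?** Protocol Appendix 4 says "the following creatinine thresholds (determined with the enzymatic method) may be used to support the evaluation of exclusion criterion 5". It lists 1.1 mg/dL for post-menstrual age 35–42 weeks and 0.88 mg/dL above 42 weeks. These equal the worst-case creatinine values of Table 8 (1.10 and 0.88), so those rows describe infants at the edge of eligibility. The documents do not show how many were enrolled.

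**The case against.** The strongest reply is that 5.2.2.4 corrects itself. It calls β the elimination rate constant and uses it in ln2/β and Ct/β, and only a log-scale slope satisfies all of these. Any standard non-compartmental analysis takes logs. SAP section 5 requires double programming, and half-lives that scale with the unit would be noticed. On this view a word is missing and no bias is to be expected.

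Much of this stands. The log was probably intended, and nothing suggests that a raw slope was planned. But the only stated estimator of a primary variable is still wrong as written. Double programming checks two programs against one specification and does not repair it.

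A second reply concerns size. The large errors need half-lives of 9–11 h, the normal rows move by 3% at most, two of the three primary variables are untouched, and the percentages hold only for µg/mL. All of that is correct. The unit point limits how the figures may be read. It does not rescue the rule, because in ng/mL the worst-case AUC0-∞ error is larger.

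A third reply is that recruitment has ended, so editing the protocol changes nothing. That has force for the protocol, but not for the SAP and the study report, which govern and describe the calculation.

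**Conclusion.** The concern holds: the definition of β is wrong as written, and neither document corrects it in the text available. Taken literally, it invalidates t1/2 and AUC0-∞, and through them CLs and, where AUC and AUMC are extrapolated, Vss.

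The numerical errors are conditional on the rule being programmed as written. They rest on noise-free one-compartment profiles, Table 8 model estimates and concentrations in µg/mL. They are not a forecast of the error in this trial. Under those assumptions AUC0-∞ is nearly unaffected at normal clearance and 27–47% too low for the slow eliminators described in Table 8, depending on the volume assumed. The literal half-life is uninformative throughout. This should be fixed: the defect is certain, actual harm is unlikely, and the correction is trivial.

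**What to change.** In SAP 5.4.1.1 add: β is minus the slope of the least-squares regression of ln(plasma concentration) on actual sampling time over the terminal post-infusion points. Say in the same place which samples count as terminal. Make the same correction in Protocol 5.2.2.4 so that the two documents agree.

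If the analysis has already been run on the log scale, state that in the SAP and the study report. If it was run on raw concentrations, recompute t1/2, AUC0-∞, CLs, Vss and the correlations that use them.

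The cost is one sentence in each document. No new data are needed, and no re-analysis if logs were used.
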